7.1.1 Cardiac precautions

All patients must have an assessment of serum potassium, magnesium, and calcium (total corrected for albumin, or ionized calcium) \leq 72 hours prior to the administration of oral panobinostat on day 1 of cycle 1 and the results must all be \geq LLN before the first dose of panobinostat is administered. Throughout the study serum biochemistry values including serum potassium, calcium, phosphorous and magnesium will be monitored closely. On any day and time in which serum potassium, calcium, phosphorous and magnesium are assessed, if the value is $<$ LLN, then the patient's potassium, calcium, phosphorous or magnesium should be immediately supplemented following the availability of that laboratory result, in order to minimize the time patients have low values. Patients must then undergo a repeat chemistry tests for repleted electrolytes (potassium, calcium, phosphorous or magnesium) to demonstrate values \geq LLN. These values must be \geq LLN before the patient is re-dosed with oral panobinostat.

Patients must be instructed to not take panobinostat if their most recent biochemistry values demonstrates potassium, calcium, phosphorous or magnesium $<$ LLN. At a minimum, potassium, magnesium, phosphorous and calcium will be checked according to the protocol. More frequent testing should be done if clinically indicated, e.g. patient has had prior low values, patient is taking medications (e.g., diuretics) that can result in lowering of their potassium, magnesium, phosphorous or calcium levels.

7.2 Treatment assignment

This is an open label, oral panobinostat maintenance therapy trial evaluating 2 different dosing schedules (cohorts A and B). Patients will be sequentially enrolled to alternating cohorts. There will be no randomization procedure involved in this study.

7.3 Treatment cycle and duration

One treatment cycle consists of oral panobinostat either (1) 20 mg PO three times per week, every other week, of a 28-day schedule, or (2) 10 mg PO daily x 7 days, every other week, of a 28-day schedule. Patients may continue treatment with oral panobinostat until they experience unacceptable toxicity that precludes further treatment, disease progression, and/or at the discretion of the investigator. The planned treatment is for a total of 12 cycles (48 weeks).

7.4 Interruption or discontinuation of treatment

For patients who are unable to tolerate the protocol-specified dosing schedule, dose adjustments are permitted in order to keep the patient on study drug. If administration of panobinostat must be interrupted because of unacceptable toxicity, drug dosing will be interrupted or modified according to rules described in [Tables 7-1, 7-2, and 7-2](#). Toxicity will be assessed using the NIH-NCI Common Terminology Criteria for Adverse Events, version 4.0 (CTCAEv4.03, (http://evs.nci.nih.gov/ftp1/CTCAE/CTCAE_4.03_2010-06-14_QuickReference_5x7.pdf)). All interruption or changes to study drug administration must be recorded.

7.4.1 Dose reduction for panobinostat

This is an open-label trial to determine the safety and tolerability of single agent panobinostat (2 dosing schedules) as maintenance therapy after autologous HCT in patients with multiple myeloma. Patients will receive either 20 mg PO TIW, every other week, every 28-days (Cohort A) or 10 mg po daily x 7 days, every other week, every 4 weeks (Cohort B). If no grade 3 or 4 toxicities occur after completing a 28-day cycle of panobinostat maintenance therapy, and all non-hematologic toxicities improved to grade 1 or better, then the next cycle of panobinostat will be initiated as long as the minimal hematologic parameters are met (ANC $\geq 1 \times 10^9/L$; hemoglobin ≥ 8 g/dl; platelets $50 \times 10^9/L$) prior to each cycle. If a subject experiences toxicity, the dose of panobinostat will be reduced to one level lower (Table 7-1) and maintained at this level for all subsequent cycles unless further toxicities occur. Panobinostat dose modifications will be made according to the toxicity grading. Once a subject's dose of panobinostat is reduced, then that dose will be the maximal dose administered. The provisional dose levels of panobinostat (LBH589) to be investigated in this study are described in Table 7-1.

Table 7-1 Provisional dose reduction for panobinostat (LBH589)

Dose level#	Panobinostat oral dose	
	Cohort A (TIW, every other week, every 4 weeks)	Cohort B (Daily x 7 days, every other week, every 4 weeks)
1 (starting dose level)	20 mg	10 mg
-1	15 mg	10 mg on days 1, 3, 5, and 7

7.4.2 Dose modifications for study drug-related toxicity (see section 7.4.3 for dose modifications for prolonged QTc):

The criteria for dose modifications for study drug-related toxicity are detailed in [Table 7-2](#).

Table 7-2 Criteria for dosing delays, dose-reductions, and re-initiation of treatment due to study drug-related toxicity (excluding QT prolongation)

Worst Toxicity CTCAE Grade* unless otherwise specified (Value)	Dose Modification Guidelines At any time during a cycle of therapy (including intended day of dosing)	
HEMATOLOGICAL TOXICITIES		
Thrombocytopenia	Grade 3 (<50 and $\geq 25 \times 10^9/L$) with bleeding and Grade 4 (< $25 \times 10^9/L$)	Temporarily discontinue panobinostat dosing until resolved to \leq grade 2, or baseline, then, restart panobinostat at reduced level as per Table 7-1

Worst Toxicity CTCAE Grade* unless otherwise specified (Value)		Dose Modification Guidelines At any time during a cycle of therapy (including intended day of dosing)
Neutropenia (ANC)	Grade 4 (ANC < 0.5 x 10 ⁹ /L)	Temporarily discontinue panobinostat dosing until resolved to ≤ grade 3, or baseline, then: 
 • If resolved within 7 days after suspending panobinostat, then restart panobinostat at an unchanged dose level • If resolved in more than 7 days after suspending panobinostat, then restart panobinostat reduced by one dose level
	Febrile neutropenia (ANC < 1.0 x 10 ⁹ /L, fever ≥ 38.5°C)	Temporarily discontinue panobinostat dosing until fever resolved and ANC ≤ grade 2, then restart panobinostat reduced by one dose level
NON-HEMATOLOGICAL TOXICITIES		
CARDIAC		
Cardiac - Prolonged QT interval**		Please refer to Section 7.4.3 .
GASTROINTESTINAL		
Diarrhea	Grade 2 (4-6 stools/day over baseline, etc) despite the use of optimal antidiarrheal medications	Temporarily discontinue panobinostat dosing until resolved to ≤ grade 1, or baseline, then restart at unchanged dose level
	Grade 3 (≥ 7 stools/day over baseline, etc) despite the use of optimal antidiarrheal medications	Temporarily discontinue panobinostat dosing until resolved to ≤ grade 1, or baseline, then restart panobinostat reduced by one dose level
	Grade 4 (life-threatening consequences, hemodynamic collapse, etc) despite the use of optimal antidiarrheal medications	Discontinue panobinostat dosing
Vomiting/Nausea***	Grade 1 & 2 not requiring treatment or controlled using standard anti-emetics	Maintain dose level
	Grade 3 or 4 vomiting or Grade 3 nausea that cannot be controlled despite the use of standard anti-emetics	Temporarily discontinue panobinostat dosing until resolved to ≤ grade 1, or baseline, then restart panobinostat reduced by one dose level

Fatigue		
Fatigue	Grade 3	Temporarily discontinue panobinostat dosing until resolved to \leq grade 2, or baseline, then: 
 • If resolved within 7 days after suspending panobinostat, then restart panobinostat at an unchanged dose level • If resolved in more than 7 days after suspending panobinostat, then restart panobinostat reduced by one dose level
	Grade 4	Temporarily discontinue panobinostat dosing until resolved to \leq grade 2, or baseline, then: 
 • restart panobinostat reduced by one dose level
HEPATIC		
Total Bilirubin	Grade 3 or 4	Temporarily discontinue panobinostat dosing until resolved to \leq grade 2, or baseline, then restart panobinostat reduced by one dose level
Note: If Grade 3 or Grade 4 hyperbilirubinemia is due to the indirect component only, and hemolysis as the etiology has been ruled out as per institutional guidelines (e.g., review of peripheral blood smear and haptoglobin determination), then reduction of one dose level and continuation of treatment is at the discretion of the Investigator.		
AST/SGOT, ALT/SGPT	> 5-10 x ULN	Temporarily discontinue panobinostat dosing until resolved to \leq grade 1 (or \leq grade 2 if liver infiltration with tumor is present), or baseline, then: 
 • If resolved within 7 days, then: 
 • restart panobinostat at unchanged dose level • If resolved in more than 7 days, then reduce panobinostat by one dose level
	> 10 x ULN	Temporarily discontinue panobinostat dosing until resolved to \leq grade 1, or baseline, then: 
 • restart panobinostat reduced by one dose level
All dose modifications should be based on the worst preceding toxicity.		
* Common Terminology Criteria for Adverse Events (CTCAE Version 4.03)		
** It is critical that electrolyte abnormalities be followed closely and corrected prior to dosing		
*** See also concomitant medication Section 7.5		

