7.1 Investigational therapy

[figure not shown]
Screening consents will be signed prior to autologous HCT to access pre-HCT stem cell graft, bone marrow and peripheral blood samples for the correlative studies. Patients will be enrolled after autologous HCT. Patients will be initiated on panobinostat maintenance therapy between day +90 and +180 after autologous HCT. Patients who develop disease progression before day +90 after autologous HCT will be ineligible for the study.

Panobinostat (also known as LBH589) will be provided by Novartis. Oral panobinostat will be supplied as 5-mg, 10-mg, 15-mg or 20-mg pink/opaque-colored, hard gelatin capsules.

Medication labels will comply with US legal requirements and be printed in English. They will supply no information about the patient. The storage conditions for study drug will be described on the medication label.

During the study, panobinostat will be administered orally as either (1) once daily dose of 20 mg (1 x 20-mg capsule) three times per week, every other week, of a 28-day schedule (Cohort A), or (2) once daily dose of 10 mg (1 x 10-mg capsule) daily x 7 days, every other week, of a 28-day schedule (Cohort B). Both cohorts will receive a maximum of 12 cycles of maintenance therapy (Figure 7-1).

Figure 7-1. Panobinostat maintenance schedule

Patients should be instructed to take their once-a-day oral dose of panobinostat at the same time each morning. Each dose of panobinostat should be taken with an 8 oz / 240 ml glass of water. Patients should be instructed to swallow the capsules whole and not chew them. Patients must avoid grapefruit or grapefruit juice and seville (sour) oranges during the entire study.

If a subject experiences toxicity, the dose of panobinostat will be reduced to one level lower (Table 7-1) and maintained at this level for all subsequent cycles unless further toxicities occur. Panobinostat dose modifications will be made according to the toxicity grading. Once a subject's dose of panobinostat is reduced, then that dose will be the maximal dose administered.

On the days of ECG monitoring, drug administration should be supervised by study center personnel and administration time should be recorded.

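### Sections 7.1 and 7.4.1 call for a lasting one-level dose reduction after toxicity, Tables 7-2 and 7-3 keep the dose unchanged for several toxicities, and no text says which governs or settles events with no row

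*Combined protocol and SAP*

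**What the plan says.** **General rule.** Section 7.4.1 says: "If a subject experiences toxicity, the dose of panobinostat will be reduced to one level lower (Table 7-1) and maintained at this level" in later cycles, subject only to further toxicity. Section 7.1 has the same sentence, beginning "If a subject experiences toxicity, the dose of panobinostat will be reduced to one level lower". The sentence names no grade, type of event or causal link to the drug. Both sections add that "Panobinostat dose modifications will be made according to the toxicity grading" and that "Once a subject's dose of panobinostat is reduced, then that dose will be the maximal dose administered".

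**Pointers to the tables.** Section 7.4 says that, when dosing must be interrupted for unacceptable toxicity, "drug dosing will be interrupted or modified according to rules described in" the tables. Section 7.4.2 places the criteria for drug-related toxicity in Table 7-2.

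**Tables.** For grade 4 neutropenia and for grade 3 fatigue, Table 7-2 says: "If resolved within 7 days after suspending panobinostat, then restart panobinostat at an unchanged dose level". For grade 2 diarrhea it says: "Temporarily discontinue panobinostat dosing until resolved to ≤ grade 1, or baseline, then restart at unchanged dose level". It also keeps the dose for AST/ALT >5-10 x ULN resolved within 7 days and for grade 1-2 nausea or vomiting that needs no treatment or is controlled. Table 7-3 resumes the prior dose after a first QTcF event resolved within 7 days.

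**Use in the analysis.** RDI for each cohort is part of the primary objective (Sections 4.1 and 13.1.3). Section 13.1 defines it as total dose received over planned full dose. It also has missed doses, reductions and delays reported by cohort, and the investigator reports the feasibility of each cohort.

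**The concern.** The same event can lead to two different doses, depending on which paragraph the treating physician follows. A reduction cannot be reversed, so one early decision fixes the patient's ceiling for the rest of the 12 cycles. The trial is open label with 15 patients per cohort, and RDI and reduction counts are among the quantities used to describe tolerability. If the text is applied unevenly, these quantities partly record how the protocol was read. The reduced level is also a larger proportional cut in Cohort B than in Cohort A, so the choice of reading alters the contrast between the two schedules as well as the level in each.

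**Working it through.** **1. The plan's own dose figure.** Section 3 gives 60 mg (A) and 70 mg (B) per week. These are treatment weeks: 20 mg x 3 = 60 and 10 mg x 7 = 70. Both reproduce.

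**2. Listed events, side by side.**

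| Event | 7.1 / 7.4.1 general sentence | Tables 7-2 / 7-3 |
|---|---|---|
| Grade 4 neutropenia, resolved within 7 days | one level lower, kept | unchanged |
| Grade 3 fatigue, resolved within 7 days | one level lower, kept | unchanged |
| AST/ALT >5-10 x ULN, resolved within 7 days | one level lower, kept | unchanged |
| Grade 2 diarrhea despite optimal medication | one level lower, kept | unchanged |
| Grade 1-2 nausea/vomiting, untreated or controlled | one level lower, kept | maintained |
| First QTcF event, resolved within 7 days | one level lower, kept | prior dose |

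In 7.4.1 the general sentence follows one about cycles without grade 3 or 4 toxicity, so it could be read as limited to grades 3 and 4. The conflict then disappears for diarrhea and nausea/vomiting but remains for grade 4 neutropenia and grade 3 fatigue. Section 7.1 lacks that lead-in.

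**3. Events with no row.** Table 7-2 covers grade 3 thrombocytopenia only with bleeding, and ANC below 1.0 only with fever or at grade 4. It has no row for afebrile grade 3 neutropenia, grade 3 thrombocytopenia without bleeding, anemia, or other grade 3 non-hematologic events such as infection or rash. The cycle-start conditions in 7.4.1 (ANC, hemoglobin, platelets, recovery of non-hematologic toxicity) say when the next cycle may begin, not at which level. The general sentence is therefore the only dose-level instruction for these events, while the table is silent.

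**4. Effect on RDI for one patient.** Inputs: Table 7-1 (level -1 is 15 mg in A, and 10 mg on days 1, 3, 5 and 7 in B), two treatment weeks per 28-day cycle, 12 cycles.

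- Planned total: A 60 x 2 x 12 = 1440 mg; B 70 x 2 x 12 = 1680 mg.
- Level -1 per treatment week: A 15 x 3 = 45 mg; B 10 x 4 = 40 mg. As a share of plan: 45/60 = 75.0% and 40/70 = 57.1%.
- Reduced from cycle 2, all doses taken: A (120 + 11 x 90)/1440 = 1110/1440 = 0.771; B (140 + 11 x 80)/1680 = 1020/1680 = 0.607.
- Reduced from cycle 7: A (6 x 120 + 6 x 90)/1440 = 0.875; B (6 x 140 + 6 x 80)/1680 = 0.786.
- Dose unchanged: at most 1.00. Most of the unchanged-dose rows first hold doses, which lowers it.

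For the cycle-2 case the gap is at most 0.23 in A and 0.39 in B.

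**5. Effect on a cohort mean.** The share of patients with such an event is not in the documents, so it is an assumption here. With share f, onset in cycle 1 and every other patient at 1.00, mean RDI = 1 - f x (1 - patient RDI).

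| Assumed f | Patients of 15 | Mean RDI, A | Mean RDI, B |
|---|---|---|---|
| 20% | 3 | 0.954 | 0.921 |
| 40% | 6 | 0.908 | 0.843 |
| 60% | 9 | 0.863 | 0.764 |

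Under the table reading of listed events both means stay near 1.00, apart from held doses.

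**The case against.** The strongest reply is that the documents already imply an order. Modifications follow grading, and 7.4 and 7.4.2 both send the reader to the tables. On that reading Table 7-1 gives the size of a step, Table 7-2 says when to take it, and the general sentence only says that a step is not undone. Naming grade 3 thrombocytopenia only with bleeding also looks deliberate. And it would be odd to reduce permanently for afebrile grade 3 neutropenia when grade 4 resolving within 7 days restarts unchanged.

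Much of this stands: it is the natural reading for listed events. But it is an inference about intent. No sentence says that the tables override the general rule. The 7.4 pointer applies only when dosing must be interrupted, and deferring to a table cannot settle events that the table omits.

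A reader might also infer more than the documents support:

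- **That nearly every patient would be reduced.** Table 2-1 has all 70 patients with an adverse event, but it counts all grades regardless of causality at 30, 45 and 60 mg. Starting doses here are 20 and 10 mg, and the general sentence does not say that every toxicity of whatever grade counts.
- **That grade 3 cytopenias have no rows at all.** Rows exist for grade 3 thrombocytopenia with bleeding and for febrile neutropenia.
- **That the frequency of unlisted events is known.** The single-agent study in Table 2-4 gives 31.6% neutropenia and 26.3% thrombocytopenia, but these pool grades 3 and 4 in relapsed/refractory patients on a weekly schedule.
- **That the completion endpoint is directly affected.** Section 13.1 counts completion of 12 cycles whatever the dose modification.

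**Conclusion.** The inconsistency is real but limited. The general sentence in 7.1 and 7.4.1 conflicts with several rows of Tables 7-2 and 7-3, and for unlisted drug-related toxicities it is the only instruction on dose level. The tables probably govern listed events, but the plan does not say so.

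The consequence falls on the dose given, on RDI and on reduction counts by cohort. RDI is descriptive and has no threshold, so no test or decision rule fails because of this. For one patient affected in cycle 1, the reading makes a difference of up to 0.23 in RDI (A) or 0.39 (B), assuming reduction from cycle 2 and all doses taken. The cohort figures depend on an assumed share of affected patients and are not forecasts. The point should be corrected, because RDI belongs to the primary objective and the remedy is small.

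**What to change.** - Reconcile 7.1 and 7.4.1 with Tables 7-2 and 7-3, and state in one place which text governs when they differ. The pointer in 7.4 names Table 7-2 twice and omits Table 7-3; correct it in the same edit.
- State which instruction on dose level applies to drug-related toxicities with no row, for example through a line for toxicities not otherwise listed. The action is for the sponsor to choose.
- If patients have already been treated, record for each reduction which text was applied, so that RDI and reduction counts can be interpreted.

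The cost is a wording amendment to Sections 7.1, 7.4 and 7.4.1 and one added line in Table 7-2. The sample size and the planned analyses do not change.

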7.4.3 Dose modifications for prolonged QTc

All cardiac events should be treated as per the local standard of care and referred to a cardiologist if clinically indicated. The localized readings of ECGs will use the Fridericia correction for QTc interval assessment: QTcF. Any final decisions concerning dose modifications or permanently discontinuing the patient from study drug due to QTcF prolongation will be based on the Investigator's clinical assessment. Any plan to deviate from these guidelines must be previously discussed and agreed upon with Novartis.

Patients must have QTcF < 470 msec to be eligible for the trial. If QTcF is \geq 470 msec or above 60 msec from baseline on a screening or pre-dose ECG, correct any electrolyte abnormalities (hypokalemia, hypomagnesemia, hypocalcemia), and conduct triplicate ECGs (5 minutes apart) and calculate average QTcF. If the average QTcF from the triplicate ECGs remains \geq 470 ms, patient must not be dosed. Pre-dose ECG monitoring is mandatory on days 1 and 5 of cycle 1, and day 1 of cycles 2 through 4. Post dose ECG (3 hours (\pm 15 minutes) post dosing) is mandatory only on days 1 and 5 of cycle 1.

If a screening, pre-dose, or post-dose ECG shows a QTcF \geq 500 ms, patient is not eligible for further treatment. If any of these mandatory ECGs show QTcF \geq 470 msec or 60 msec above baseline, dosing should be held and the above specified measures including follow-up triplicate ECGs and correction of electrolyte abnormalities should be performed. If QTcF abnormality resolves, patients should resume treatment and have QTcF checked pre-dose on day 1 of each cycle for at least the next 3 subsequent cycles. Additional QTcF monitoring should be performed if clinically indicated. If a patient cannot be dosed due to prolonged QTcF for more than 7 days since last dose, patient must be discontinued from study treatment.

Table 7-3 Dose Reductions for QTc Prolongation

Time Point	Average QTcF*	Action
Screening and pre-dose cycle 1 day 1	\geq 470 msec	Delay treatment Correct any electrolyte abnormal values ** and repeat ECG, if the average QTcF \geq 470 msec, do not dose
	Above 500 msec	Patient is not eligible
Pre-dose cycle 1 day 5 Pre-dose day 1 of subsequent cycles	\geq 470 msec or above 60 msec from baseline for any pre-dose ECG after the patient has commenced treatment***	Omit dose If unresolved within 7 days, discontinue treatment If resolved within 7 days, resume treatment at prior dose for initial occurrence or at reduced dose if recurrent
	Above 500 msec	Permanently discontinue treatment
*QTcF: Heart rate corrected QT interval using the Fredericia formula: $QTc = QT/RR^{0.33}$ **: serum potassium, magnesium, calcium, ***If a single pre-dose QTcF is \geq 470 msec or 60 msec from baseline, subsequent ECGs should be performed in triplicate		

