For the QOW schedule post-baseline increased values of >30 and ≤60 msec were observed in 16 (16.7%) patients. Post-baseline increase of >60 msec was less frequent (4 patients, 4.2%). Absolute QTcF prolongation values of 450 msec to 480 and of >480 to 500 msec were reported in 9 patients (9.6%) and in 1 patient (1.0%), respectively. Absolute QTcF prolongation above 500 msec was not observed.

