10. Prior HDAC, DAC, HSP90 inhibitors or valproic acid for the treatment of cancer is allowed.

Exclusion criteria (panobinostat maintenance)

1. Patients who have purely non-secretory multiple myeloma (i.e., the absence of a measurable protein in serum by electrophoresis and immunofixation and the absence of Bence-Jones protein in the urine defined by use of electrophoresis and immunofixation)
2. Prior allogeneic HCT
3. Prior solid organ transplant requiring immunosuppressive therapy
4. Patients who will need valproic acid for any medical condition during the study or within 5 days prior to first panobinostat treatment
5. Impaired cardiac function or clinically significant cardiac diseases, including any one of the following:
 - History or presence of sustained ventricular tachyarrhythmia. (Patients with a history of atrial arrhythmia are eligible but should be discussed with Novartis prior to enrollment)
 - Any history of ventricular fibrillation or torsade de pointes
 - Bradycardia defined as HR < 50 bpm. Patients with pacemakers are eligible if HR \geq 50 bpm.
 - Screening ECG with a QTc > 470 msec
 - Right bundle branch block + left anterior hemiblock (bifascicular block)
 - Patients with myocardial infarction or unstable angina ≤ 12 months prior to starting study drug
 - Other clinically significant heart disease (e.g., CHF NY Heart Association class III or IV, uncontrolled hypertension, history of labile hypertension, or history of poor compliance with an antihypertensive regimen)
4. Patients with diarrhea > CTCAE grade 2
5. Other concurrent severe and/or uncontrolled medical conditions (e.g., uncontrolled diabetes or active or uncontrolled infection) including abnormal laboratory values, that could cause unacceptable safety risks or compromise compliance with the protocol
6. Patients using medications that have a relative risk of prolonging the QT interval or inducing torsade de pointes (see Table 17-1) if treatment cannot be discontinued or switched to a different medication prior to starting study drug
7. Patients who have received targeted agents within 2 weeks or within 5 half-lives of the agent and active metabolites (whichever is longer) and who have not recovered from side effects of those therapies.

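### The text of Section 7.4.3 ends treatment at QTcF of 500 msec or more, but Table 7-3 does so only strictly above 500, so one reading can lead to two different actions

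*Combined protocol and SAP*

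**What the plan says.** **At 500 msec.** The text of Section 7.4.3 gives a categorical rule: "If a screening, pre-dose, or post-dose ECG shows a QTcF" of 500 ms or more, "patient is not eligible for further treatment". Table 7-3 sets its cut-off strictly above 500 msec. At screening and before the first dose the consequence is ineligibility. Before dosing on cycle 1 day 5 and on day 1 of later cycles the instruction is "Permanently discontinue treatment". The table's QTcF column is headed as an average, yet its on-treatment 470 row applies "for any pre-dose ECG after the patient has commenced treatment". The table has no post-dose row, although the text covers post-dose ECGs.

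**At 470 msec.** Section 7.4.3 says "Patients must have QTcF < 470 msec to be eligible for the trial", and Table 7-3 withholds dosing if the average on repeat is 470 or more. Exclusion 5 in Section 6.1.3 lists "Screening ECG with a QTc > 470 msec". The note to Table 8-2 requires a mean baseline QTc of 470 or less.

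**Who decides.** Sections 7.4.3 and 8.3.6 leave final QTcF decisions to the investigator, but a planned departure from the guidelines has to be agreed with the supporting company beforehand.

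**The concern.** These thresholds decide whether a patient on a drug with known QTcF prolongation stays on treatment, and the action at 500 is permanent. The protocol sends staff to the two versions by different routes. Table 7-2 refers QT prolongation to Section 7.4.3 as a whole, and footnote a of the ECG schedule in Table 8-2 points to Table 7-3. Two careful readers could take opposite actions on the same ECG, and following either rule could be recorded as a departure from the other. What is at stake is consistent application of a safety rule and clean deviation reporting. No material effect on the 12-cycle completion endpoint is claimed.

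**Working it through.** The plan gives no figure to reproduce here, so the check sets the rules side by side at the boundary values and then bounds the frequency.

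**Step 1. Exactly 500 msec.** A value of 500 is not above 500, so in Table 7-3 it falls in the row for 470 or more.

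| Time point | Text of 7.4.3 | Table 7-3 |
|---|---|---|
| Screening or pre-dose cycle 1 day 1 | No treatment | Delay, correct electrolytes, repeat; may be dosed if the average is then below 470 |
| Later pre-dose ECG | No further treatment | Omit dose; resume if resolved within 7 days, at the prior dose on first occurrence |

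The two columns differ at both time points whatever the column header means. The table's cut-off is spelled out in words and the inequality signs in neighbouring rows survived, so this is not a symbol lost in PDF conversion.

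**Step 2. Single reading against average (conditional).** Suppose the header governs the 500 rows. Take an illustrative triplicate of 505, 488 and 492:

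- mean = (505 + 488 + 492) / 3 = 1485 / 3 = 495 msec.

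The text ends treatment because one ECG is at least 500. The table, read on the mean of 495, does not. If the header does not govern, this limb disappears and only Step 1 remains.

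**Step 3. Exactly 470 msec at entry.** Exclusion 5 is not triggered at 470, and the Table 8-2 note is satisfied. Section 7.4.3 is not satisfied, because it requires a value below 470, and it forbids dosing while the triplicate average is 470 or more. Section 6.1.3 requires every criterion to be met, so the strictest rule prevails and a patient with a confirmed average of 470 is not dosed.

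**Step 4. Frequency of values at or above 500.** The closest data are the every-other-week results in Section 2.1.5, whose doses are not stated: "Absolute QTcF prolongation above 500 msec was not observed", and values in the two bands below, 450 to 480 and "of >480 to 500 msec were reported in 9 patients (9.6%) and in 1 patient (1.0%), respectively".

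- Denominator, back-calculated: 16 / 0.167 = 95.8. Only n = 96 reproduces 16 (16.7%), 4 (4.2%) and 1 (1.0%). The 9 (9.6%) fits 94, so that band has a slightly smaller base; it is not used here.
- Above 500: 0/96, exact (Clopper-Pearson) 95% upper limit = 1 − 0.025^(1/96) = 3.8%; 30 × 0.0377 = 1.1 patients.
- At or above 500: at least 0 (the one patient in the top band was below 500) and at most 1 (that patient was at exactly 500). This assumes the band includes 500, as in Table 2-3.
- 1/96 = 1.04%, exact 95% CI 0.03% to 5.67%; 30 × 0.0104 = 0.3, with upper limit 30 × 0.0567 = 1.7 patients.

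**Step 5. Cross-check at 20 mg.** Table 2-3 covers the denser every-week schedule at Cohort A's dose. It shows 1/309 above 500 and 5/309 above 480 up to 500. So between 1 and 6 of 309 reached 500 or more: 30 × 1/309 = 0.1 to 30 × 6/309 = 0.6 patients.

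Steps 4 and 5 bound how many patients could meet the text's rule. They do not count how many the two rules would treat differently. The documents do not report values of exactly 500 or separate single readings from averages, so that number cannot be computed.

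**The case against.** The strongest reply is that the certain conflict covers a single value and exposes nobody to a dose at that value: with QTcF confirmed at 500 the text stops treatment and the table withholds it. They differ only on starting or resuming later. That is correct, and it limits the severity. It does not remove the conflict, because one rule is permanent and the other reversible.

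It can also be said that the categorical text should lead, since footnote a of Table 8-2 calls the contents of Table 7-3 recommended, and that the investigator decides in any case. This gives a hint about precedence but no statement of it. The need for prior agreement to deviate makes it more important to know which rule is the guideline.

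The averaging limb is open to challenge, because the on-treatment 470 row and its footnote are triggered by a single reading. It stands only as a conditional point.

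A reader might infer from exclusion 5 and the Table 8-2 note that the protocol admits patients at exactly 470, with two places set against two. The documents do not support that. Passing one exclusion admits nobody, the Table 8-2 note states a necessary condition, and no rule permits dosing at a confirmed average of 470. What remains is inconsistent wording.

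**Conclusion.** The concern holds for 500 msec. At exactly 500, the text of Section 7.4.3 and Table 7-3 prescribe different actions, and no order of precedence is stated. If the table's averaging header governs its 500 rows, they also differ when a single reading is 500 or more and the triplicate mean is not above 500.

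The expected size is very small: on the every-other-week data, 0 to 0.3 of 30 patients reaching 500 or more (upper confidence limit 1.7). This assumes that the top reported band includes 500 and that those patients resemble the trial's. The entry wording at 470 is a secondary matter of harmonisation.

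A reader might go further and infer that patients could be dosed while at 500, or that the primary endpoint is compromised. The documents support neither. The change is still worth making, because it concerns a permanent cardiac stopping rule and can be settled with a few words.

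**What to change.** Make one amendment that adopts the stricter rule already in the text of Section 7.4.3.

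1. **Table 7-3, screening and pre-dose cycle 1 day 1:** any single screening or pre-dose ECG with QTcF ≥ 500 msec, not eligible.
2. **Table 7-3, on treatment:** any single pre-dose or post-dose ECG with QTcF ≥ 500 msec, permanently discontinue. Add the cycle 1 day 1 and day 5 post-dose ECGs to this row's time points.
3. **Table 7-3, column header:** change it to QTcF, and state that the average applies only to the repeat triplicate for values ≥ 470 msec.
4. **Entry cut-off:** change exclusion 5 to QTcF ≥ 470 msec and the Table 8-2 note to QTcF < 470 msec, confirmed by the existing triplicate average.

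No ECGs are added, because the post-dose recordings and the triplicate step are already in the plan. The costs are routine review of the amendment by the supporting company and the IRB, and the chance that a rare patient is stopped on one outlying reading, which the text of 7.4.3 already requires.
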